6. SAFETY

All safety analyses will be descriptively summarized and based on the Safety analysis set. There will be no formal statistical testing for any safety endpoint. Refer to Section 2.4 for further details regards subgroup analysis, per the analyses detailed below.

6.1. Adverse Events

6.1.1. Definitions

Coding of AE

The verbatim terms used in the eCRF by investigators to identify AEs will be coded using the Medical Dictionary for Regulatory Activities. Events are looked at on the level of their preferred term.

Emergent Adverse Event

Emergent AEs are AEs with onset after first study medication intake or that are a consequence of a pre-existing condition that has worsened since baseline. All reported emergent AEs will be included in the analysis. For each AE, the percentage of subjects who experience at least 1 occurrence of the given event will be summarized by treatment group.

Emergent AEs are categorized as related to study medication, if assessed, by the investigator, as ‘possibly’, ‘probably’, or ‘very likely’ related to the study medication.

Phase Allocation of AE

Adverse events present in the SDTM database are allocated to analysis phases based on their start date (refer to Section 2.1). If the start date of an event falls between (or on) the analysis phase start date and before- or on analysis phase stop date, the AE is attributed to that analysis phase (emergent principle).

Incomplete dates (i.e. time and/or day and/or month and/or year missing) are imputed according to the rules in Section [2.5](#).

6.1.2. Adverse Events of Special Interest

In addition to RSV-related complications, detailed in Section [5.4](#), the following adverse events of special interest are defined (refer to [Table 24: Cardiac Events Potentially Related to QT Prolongation](#)):

Table 24: Cardiac Events Potentially Related to QT Prolongation

MedDRA Preferred Term (PT)	MedDRA Code
Electrocardiogram QT interval abnormal	10063748
Electrocardiogram QT prolonged	10014387
Long QT syndrome	10024803
Long QT syndrome congenital	10057926
Torsade de pointes	10044066
Ventricular tachycardia	10047302
Cardiac arrest	10007515
Cardiac death	10049993
Cardiac fibrillation	10061592
Cardio-respiratory arrest	10007617
Electrocardiogram repolarisation abnormality	10052464
Electrocardiogram U wave inversion	10062314
Electrocardiogram U wave present	10057913
Electrocardiogram U-wave abnormality	10055032
Loss of consciousness	10024855
Electrocardiogram QT interval abnormal	10063748
Sudden cardiac death	10049418
Sudden death	10042434
Syncope	10042772
Ventricular arrhythmia	10047281
Ventricular fibrillation	10047290
Ventricular flutter	10047294
Ventricular tachyarrhythmia	10065341

6.1.3. Analysis Methods

Emergent adverse events will be summarized by body system, preferred term and treatment group (including a column for total JNJ-8678).

A summary will be provided for the following emergent adverse events by analysis phase (overall analysis treatment- and follow-up phase) and by analysis treatment phase only:

- any adverse events,
- serious adverse events,
- deaths due to AE (based on outcome = fatal),
- AEs at least Grade 3 or Grade 4 toxicity,
- AEs at least possibly related to study medication,
- AEs at least Grade 2 toxicity AND at least possibly related to study medication,
- AEs for which study medication was permanently stopped,
- AEs for which study medication was interrupted (action taken with study drug = drug interrupted),
- AEs for which study was discontinued prematurely,
- serious adverse events that were at least possibly related to study medication.

Aforementioned will be presented as an overview, overall and by each of the subgroups noted in Section 2.4. Presentation as incidence table or listing will depend on the number

of events identified, as detailed in a separate document (data presentation specifications [DPS]).

As part of safety, RSV-related complications during the overall analysis treatment- and follow-up phase, based on investigator's assessment, will be summarized descriptively. As RSV-related complications are analyzed as part of exploratory efficacy endpoints, refer to Section 5.4 for details regards analysis and presentation of RSV-related complications.

Emergent cardiac events potentially related to QT prolongation, identified based on MedDRA preferred term code, will be summarized descriptively by analysis phase (overall analysis treatment- and follow-up phase) and by analysis treatment phase only if there are at least 5 events identified across all treatment groups.

Listings will be provided for at least the following, depending on the number of events:

- All adverse events
- Serious adverse events
- AEs leading to death (based on outcome = fatal)
- Toxicity Grade 3 to 4 adverse events
- AEs for which study medication was permanently stopped
- AEs for which study medication was interrupted
- AEs for which study was discontinued prematurely

6.2. Clinical Laboratory Tests

6.2.1. Definitions

Laboratory parameters of hematology, serum chemistry, and urinalysis will be investigated. Analyses will be based on International System of Units (SI) converted values as available in the database.

Toxicity grades and abnormalities for laboratory parameters

The laboratory abnormalities will be determined according to the Division of Microbiology and Infectious Diseases (DMID) pediatric toxicity tables (see [Attachment 1](#)). Toxicity grades where available per parameter and age group, will be provided by the central laboratory and will be used in the analysis. In case no DMID toxicity grades are defined for a test and/or age group, the abnormalities (above/below normal range) will be used.

In determining toxicity grades/abnormalities for each subject the following rules are applied:

- Worst grades/abnormalities are determined over the whole observational period, per phase (analysis treatment, analysis follow-up [separately] and in combination analysis treatment + follow-up phase), including scheduled and unscheduled measurements.
- The abnormalities "abnormally low" and "abnormally high" are considered equally important, i.e. if a subject has as well an abnormally low as an abnormally high value post-baseline, both abnormalities are shown in the tables. This means that the sum of the percentages can be more than 100%.

- If, for a specific test, the grading list provides distinct limits for abnormally low (=hypo) values as well as for abnormally high (=hyper) values, this test should be repeated for hyper- and hypo- limits separately in cross-tabulations.

For subjects enrolled under original protocol dated 13 July 2018, coagulation function will be monitored during this clinical study through evaluation of partial thromboplastin time (PTT) and activated partial thromboplastin time (aPTT) in seconds, and calculation of the International normalized ratio by the central lab. Grading of abnormalities in these parameters (PT and PTT) will be based on the DMID Pediatric Toxicity Table (see [Attachment 1](#)). Coagulation will not be evaluated in subjects enrolled as of protocol amendment 1 (dated 14 May 2019).

Post-amendment #4 (dated 26 May 2020), levels of potassium and magnesium will be determined by the central laboratory. In case of hypokalemia or hypomagnesemia at Screening or Day 8, the levels of potassium and magnesium are to be monitored locally and corrected to prevent cardiac disturbances. During the study locally determined potassium and/or magnesium levels need to be recorded in the eCRF as unscheduled laboratory visits/assessments. Data will be listed.

The eGFR will be calculated/reported by the central lab (Schwarz formula) and used as such in the analysis.

Emergent definition for toxicity grades and abnormalities

An abnormality (toxicity grade or abnormality based on normal ranges) will be considered emergent if it is worse than the baseline abnormality. If the baseline abnormality is missing, the abnormality is always considered as emergent. A shift from “abnormally low” at baseline to “abnormally high” post baseline (or vice versa) is also emergent. The emergence definition applies regardless of analysis phase and within each analysis phase.

In case of missing date or partial dates

Laboratory records with missing assessment date- or time- parts (any: day, month or year) will not be used in descriptive statistics, unless the scheduled target day or time is known, and a unique analysis phase allocation is possible taking this additional information into account. These assessments will be allocated to the correct phase using the available date/time information, and the information in their assessment schedule. In case it is not possible to assign a unique analysis phase (e.g. unscheduled timepoints), the assessment will be assigned to all possible active analysis phases based on the available date and time information. These cases will be flagged in the respective listings.

Imputations of numerical values expressed as characters

In case a laboratory test result is *censored* (no numeric value is available, but only a verbatim term), the following rules are applied:

- ‘<x’ or ‘>x’: a numeric value will be imputed by a value exceeding the cut-off value with one unit
- ‘≤x’ or ‘≥x’: imputation by x.

This also applies to normal limits expressed as such.

No such imputations will be done for urinalysis parameters as these are usually character/categorical expressions.

6.2.2. Analysis Methods

Descriptive statistics (mean, standard deviation, median and range) will be provided for the clinical laboratory tests at each scheduled visit. Changes from baseline will be summarized by treatment group. Incidence of clinical laboratory tests that meet toxicity grades or criteria for abnormality will be tabulated for each treatment group.

A cross-tabulation of the worst toxicity/abnormality versus baseline toxicity/abnormality will be presented for the combination of analysis treatment- and follow-up phase and for analysis treatment phase only. This table will also show the number (n) and percentage (%) of subjects per worst toxicity/abnormality, the number (n) and percentage (%) of subjects per emergent worst toxicity/abnormality and the cumulative number of subjects per emergent toxicity/abnormality or worse.

Mean \pm SE graphs over time for the actual values and change from baseline will be generated for all hematology and clinical chemistry tests by treatment group and by age group as assigned at Screening.

A listing of abnormal individual subject hematology, blood coagulation and clinical chemistry values from scheduled and unscheduled timepoints will be provided. This listing will include all other timepoints for the corresponding subject/parameter. Grade 2 or higher toxicity laboratory values will be listed separately. Urinalysis results will be listed only.

6.3. Vital Signs and Physical Examination Findings

6.3.1. Definitions

Systolic (SBP) and diastolic blood pressure (DBP), HR, RR, oxygen saturation and body temperature will be investigated. A directed physical examination (DPE) will be performed at several timepoints throughout the study, which includes respiratory system, nose, ear, throat, facial, and neck lymph nodes, and skin examination. Note that heart rate, respiratory rate, oxygen saturation (SpO_2) and body temperature are also analyzed as part of efficacy endpoints.

Definitions Grades/Abnormalities

Two sets of abnormality codes for SBP, DBP, HR, RR and oxygen saturation will be defined, as indicated in [Table 25](#) and [Table 26](#). Vital signs abnormalities will be identified based on subject's age at the time of the assessment and as follows:

- Worst grades/abnormalities are determined over the whole observational period and for each analysis phase separately, including post-baseline scheduled and unscheduled measurements of that analysis phase.
- The abnormalities 'abnormally low' and 'abnormally high /grades are considered equally important, i.e. if a subject has as well an abnormally low as an abnormally

high or graded value post-baseline, both abnormalities are shown in the tables. This means that the sum of the percentages can be more than 100%.

Table 25: Normal Ranges – Below/Normal (including extremes)/Above

Parameter (unit)	Age class				
	0 – 3 months	3 – 6 months	6 – 12 months	1 – 2 years	2- <3 years
Diastolic BP (mmHg)	45 - 55	50 - 65	55 - 65	55 - 70	45 - 60
Systolic BP (mmHg)	65 -85	70 - 80	80 - 100	90 - 105	85 - 100
Heart rate HR (bpm)	100 - 150	90 - 120	80 - 120	70 - 110	95 - 125
Respiratory rate	35 - 55	30 - 45	25 - 40	20 - 30	22 - 30
Oxygen saturation	≥96	≥96	≥96	≥96	≥96
SpO ₂ (%)					

Table 26: Relevant Abnormalities – Abnormally Low/Normal/Abnormally High

Parameter (unit)		Age class			
		0 – 3 months	3 – 12 months	1 – 2 years	2- <3 years
Diastolic BP (mmHg)	abnormally low	<35	<40	<40	<40
	abnormally high	>65	>85	>90	>70
Systolic BP (mmHg)	abnormally low	<60	<60	<75	<80
	abnormally high	>110	>110	>120	>110
Heart rate HR (bpm)	abnormally low	<80	<70	<60	<90
	abnormally high	>180	>150	>140	>130
Respiratory rate	abnormally low	<25	<20	<18	<20
	abnormally high	>70	>60	>50	>35
Oxygen saturation	abnormally low	<92	<92	<92	<92
SpO ₂ (%)					

Abnormality codes for body temperature are defined, as indicated in [Table 27](#).

Table 27: Abnormalities for Body Temperature

Abnormality Code	Temperature (°C)				
	Tympanic	Forehead	Oral	Rectal	Axillary
Abnormalities on actual values					
Normal	≤ 37.8	≤ 38.0	≤ 38.0	≤ 37.2	≤ 38.0
Abnormally high	> 37.8	>38.0	>38.0	>37.2	>38.0

Emergence definition for grades/abnormalities

A grade/abnormality will be considered emergent if it is worse than baseline. If baseline is missing, the grade/abnormality is always considered as emergent. A shift from ‘abnormally low’ at baseline to ‘abnormally high’ post baseline (or vice versa) is also emergent. The emergence definition applies regardless of analysis phase and within each analysis phase.

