2.1. Visit Windows and Phase Definitions

2.1.1. Analysis Phase Definitions

Analysis phases will be constructed as defined in [Table 2](#).

Table 2: Analysis Phases

Analysis Phase [number]	Start Date/Time	End Date/Time
Screening [1]	00:00 of the date of signing the informed consent form *	1 minute before the first study drug administration in the trial
Treatment [2]	Date/time of first study drug administration in the trial	23:59 of the last day of treatment + 3 days or 23:59 of the cut-off date for the IA, whichever comes first
Follow-up [3]	1 minute after the End of Treatment Phase	23:59 of the day of trial termination (date of last contact) or 23:59 of the cut-off date for the IA, whichever comes first

* For some sites, diagnostic ICF (Dx ICF) is required if RSV infection testing is not part of SOC or the SOC RSV diagnostic assay is not approved for use in the study. The earliest date between Dx ICF and main ICF will be used as a reference.

Assessments will be assigned to analysis phases based on their date/time, but seconds will be ignored overall. If the day part of the start date of the assessment is present but the time part is missing, the assessment will be treated as if it started at 00:00 on the day of the event (unless for Adverse Events see details in [Section 6.1](#)). If the day part of the end date of the assessment is present but the time part is missing, the assessment will be treated as if it happened at 23:59 on the day of the event. No formal imputation will be done, these rules will only be applied to allocate assessments to analysis phases.

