^{\$} Post-baseline (excluding assessments completed within 1h post-first dose of study drug on Day1 which are considered as baseline).

From Day 15 onwards, relative day (adjusted by timeframe as in the table) will be used to define analysis visits. In case there is more than one assessment per analysis visit, the one closest to the target will be used for the summary table per analysis visit. If more than one is equally close, then the last one will be considered in the analysis.

Note: in case there is an assessment on Day 14 not covered in the 312h window, it will not be used in by-visit summary tables and figures but will only be shown in individual listings and figures. Such assessments will contribute to time to event analyses, identification of abnormalities etc., as relevant.

For analyses for which we need at most one assessment per day (e.g. for summarizing combined in- and outpatient data captured by the clinician), we take the worst over 24 hours according to **Table 6**.

Table 6: Worst per Day

Analysis time	Primary Selection ("worst hourly")	Secondary Selection* ("worst daily") TIME INTERVAL (Day) [TARGET TIMEPOINT (Day)]
Baseline		
Day 2	Worst [12h; 24h]	
Day 3	Worst [36h; 48h]	3 [3]
Day 4	Worst [60h; 72h]	
Day 5	Worst [84h; 96h]	4-6 [5]
Day 6	Worst [108h; 120h]	
Day 7	Worst [132h; 144h]	
Day 8	Worst [156h; 168h]	8-9 [8]

Table 6: Worst per Day

Analysis time	Primary Selection ("worst hourly")	Secondary Selection*
		("worst daily") TIME INTERVAL (Day) [TARGET TIMEPOINT (Day)]
Day 9	Worst [180h; 192h]	
Day 10	Worst [204h; 216h]	
Day 11	Worst [228h; 240h]	
Day 12	Worst [252h; 264h]	
Day 13	Worst [276h; 288h]	
Day 14	Worst [300h; 312h]	13-15 [14]
Day 15	Worst as per relative day (2 AM-1:59 AM) Relative day	
Day 16	Worst as per relative day [16] (2 AM-1:59 AM)	
Day 17	Worst as per relative day [17] (2 AM-1:59 AM)	
Day 18	Worst as per relative day [18] (2 AM-1:59 AM)	
Day 19	Worst as per relative day [19] (2 AM-1:59 AM)	
Day 20	Worst as per relative day [20] (2 AM-1:59 AM)	
Day 21	Worst as per relative day [21] (2 AM-1:59 AM)	18-24 [21]
Day 28	25 to $+\infty$ [28]	25 to $+\infty$ [28]

* For ClinRO and Clinical Evaluation only: the secondary selection approach will be considered in the analysis if no record is assigned to Day 3, Day 5, Day 8, Day 14 and/or Day 21 according to the rules in the primary selection column in [Table 6](#) (for subjects in Cohort 1 after hospital discharge, or for Cohort 2 subjects).

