6.3.2. Analysis Methods

Descriptive statistics (mean, standard deviation, median and range) will be provided for the vital signs at each scheduled visit. Changes from baseline will be summarized by treatment group. Incidence of vital signs tests that meet criteria for abnormality will be tabulated for each treatment group.

A cross-tabulation of the worst grade/abnormality versus baseline will be presented for the combination of analysis treatment- and follow-up phase and for analysis treatment phase only. This table will also show the number (n) and percentage (%) of subjects per worst grade/abnormality, the number (n) and percentage (%) of subjects per emergent worst grade/abnormality. For Respiratory rate, heart rate and body temperature, the maximum value will be considered as the worst grade/value while for oxygen saturation, the lowest value will be considered the worst one. In determining the maximum body temperature, all temperature assessments will be considered regardless of whether obtained during on-site visit or measured by caregiver and reported in handheld device.

Mean \pm SE graphs over time for the actual values and changes from baseline will be generated and presented by treatment group and by age group as assigned at Screening.

A listing of abnormal individual subject vital signs values from scheduled and unscheduled timepoints will be provided. This listing will include all other timepoints for the corresponding subject/parameter.

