6.4.1. Definitions

Definitions and Abnormalities

The ECG abnormalities will be defined as indicated in [Table 28](#). ECG abnormalities will be identified based on subject's age at the time of the assessment and as follows:

- Worst grades/abnormalities are determined over the whole observational period and for each analysis phase separately, including post-baseline scheduled and unscheduled measurements of that analysis phase.
- The abnormalities 'abnormally low' and 'abnormally high'/grades are considered equally important, i.e. if a subject has as well an abnormally low as an abnormally high or graded value post-baseline, both abnormalities are shown in the tables. This means that the sum of the percentages can be more than 100%.

Table 28: ECG Abnormalities

Parameter (unit)	Age class	Abnormally low	Abnormally high
PR (msec)	0 - 2 years	NA	>150
	2 - <3 years	<100	>150
QRS (msec)	0 - 2 years	NA	>79
	2 - <3 years	<40	>79
QT (msec)	0 - 2 years	NA	>500
	2 - <18 years	<320	>450
RR (msec)	0 - 3 months	<333	>750
	3 - 12 months	<400	>860
	1 - 2 years	<430	>1000
	2 - <18 years	<600	>1200
Abnormalities on the changes from baseline (ΔQTc)			
		Abnormality Code	Criteria
QT corrected		Borderline QTc change	30 ms < ΔQTc < 60 ms
		Abnormally high QTc change	ΔQTc > 60 ms
Abnormalities on actual QTcF values			
QT corrected Fridericia's Correction Formula	Abnormally high QTcF value		450 ms < QTcF \leq 480 ms
			480 ms < QTcF \leq 500 ms >500 ms

Emergent definition for abnormalities

An abnormality will be considered emergent if it is worse than baseline. If baseline is missing, the abnormality is always considered as emergent. A shift from ‘abnormally low’ at baseline to ‘abnormally high’ post-baseline (or vice versa) is also emergent. The emergence definition applies regardless of analysis phase and within each analysis phase.

TriPLICATE ECG ASSESSMENTS

If not available from the central ECG laboratory: for timepoints on which triplicate ECGs apply (expected for all timepoints), a mean value per triplet cluster, will be calculated per timepoint before any further handling. This mean value will be used through the entire analysis. In the analysis dataset, the time of the first triplet member will be retained for this average record.

Rounding

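### When a child crosses an age class and a limit tightens, an unchanged vital sign or ECG value is counted as an emergent abnormality

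*SAP*

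**What the plan says.** Section 6.3.1 identifies vital-sign abnormalities from the subject's "age at the time of the assessment and as follows". Section 6.4.1 does the same for ECG. The limits are stepped by age class: in Tables 25 and 26 for diastolic and systolic pressure, heart rate and respiratory rate; in Table 28 for the RR interval and, at 2 years only, for QT and the lower limits of PR and QRS. The title of Table 25, "Below/Normal (including extremes)/Above", makes its range ends normal.

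The emergence rule for vital signs is "A grade/abnormality will be considered emergent if it is worse than baseline", and for ECG "An abnormality will be considered emergent if it is worse than baseline". Both sections add that a move from abnormally low at baseline to abnormally high later also counts. On output, Section 6.3.2 states: "A cross-tabulation of the worst grade/abnormality versus baseline will be presented". That table also carries the number and percentage of subjects with an emergent worst abnormality, and Section 6.4.2 plans the same for ECG.

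**The concern.** Baseline is itself an assessment, so its code comes from the limits for the child's age at baseline, while a later code comes from the limits for the later age. The emergence rule compares these two codes without putting them on one scale. In a trial of infants from 28 days of age, followed for about four weeks, some children will have a 3-month, 6-month, 1-year or 2-year boundary between the two assessments. For them a change of code can come from the table and not from the child. At stake is the emergent n (%) in the vital-sign and ECG safety tables, which would include children whose values did not move.

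**Working it through.** The SAP states no figure on this point, so there is none to reproduce. The check has three parts.

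**1. Unchanged values that become emergent.** Each whole-number value was coded with the limits on either side of a boundary. A value that is normal before and abnormal after is flagged without having changed.

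| Table, boundary | Parameter | Limit before, then after | Values falsely flagged | Share of earlier normal range |
|---|---|---|---|---|
| 26, 3 months | Heart rate, high | >180, >150 | 151–180 | 30 of 101 values (80–180) = 30% |
| 26, 3 months | Respiratory rate, high | >70, >60 | 61–70 | 10 of 46 (25–70) = 22% |
| 25, 3 months | Heart rate, upper | 150, 120 | 121–150 | 30 of 51 (100–150) = 59% |
| 25, 6 months | Systolic pressure, lower | 70, 80 | 70–79 | 10 of 11 (70–80) = 91% |
| 28, 2 years | RR interval (ms), low | <430, <600 | 430–599 | 170 of 571 (430–1000) = 30% |

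The last column counts values, not children. In the systolic row, the normal ranges before and after 6 months (70–80, then 80–100) share only the value 80. In the last row, an RR interval of 500 ms is a heart rate of 60,000/500 = 120 bpm, which Table 25 calls normal at that age (95–125).

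**2. Direction of the steps in Table 26.** There are 8 limits (low and high for four parameters) at 3 boundaries, so 24 steps.

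- 3 months: 3 tighten, 3 relax, 2 unchanged.
- 12 months: 3, 4 and 1.
- 2 years: 7, 0 and 1.
- Total: 13 tighten, 7 relax, 4 unchanged.

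**3. How many children are exposed.** A child aged *a* days on Day 1 is aged *a* + *d* − 1 on Day *d*, so for a boundary above the youngest ages, *d* − 1 starting ages cross it by Day *d*. The boundaries at 92 and 183 days follow the dosing groups in Section 1.2; 366 and 731 days are assumed for 1 and 2 years. The SAP gives no age distribution, so uniform ages are assumed over 28–1,096 days (1,069 ages) or, for a younger population, 28–365 days (338 ages). Clinic days are taken from the Table 6 footnote in Section 2.1.4 ("if no record is assigned to Day 3, Day 5, Day 8, Day 14 and/or Day 21"). The analysis treatment phase ends at "23:59 of the last day of treatment + 3 days", which is Day 10 or 11 if dosing ends on Day 7 or 8.

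- Dosing group 1 (28–91 days, 64 ages), crossing 3 months: Day 8, 7/64 = 10.9%; Day 10, 9/64 = 14.1%; Day 11, 10/64 = 15.6%; Day 21, 20/64 = 31%.
- All children, any Table 26 boundary: Day 8, 21/1,069 = 2.0% or 14/338 = 4.1%; Day 21, 60/1,069 = 5.6% or 40/338 = 11.8%.
- All children, any Table 25 boundary: Day 8, 28/1,069 = 2.6% or 21/338 = 6.2%; Day 21, 80/1,069 = 7.5% or 60/338 = 17.8%.

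Of the 294 planned subjects, the Table 26 shares at Day 21 are about 17 to 35 children. Only those whose value lies between the two limits can be flagged without a change.

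**The case against.** Four points can be made against this.

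- **The rule may compare values, not codes.** The laboratory rule in Section 6.2.1 refers to the baseline abnormality, while the vital-sign and ECG rules refer only to baseline. Section 6.3.2 also treats the maximum heart rate and respiratory rate as the worst value, so an unchanged 160 bpm is arguably not worse. It is true that the comparison of codes is inferred. It is still the direct reading, because the rule speaks of a shift from low to high and the output cross-tabulates abnormality classes. The value reading would not remove the problem either: a change from 160 to 161 bpm across the 3-month boundary would still be flagged.
- **Age at assessment was a deliberate choice**, clarified in Amendment 3, and any stepped limits jump at a boundary. This stands, and the choice is sound for the abnormality itself. The emergence rule was not adapted to it.
- **The effect is contained.** "There will be no formal statistical testing for any safety endpoint", and the change-from-baseline summaries and the listings, which show all timepoints for the child and parameter, reveal an unchanged value. This stands and limits the severity.
- **A relaxed limit does not show a missed event.** A reader might infer that the rule also hides real worsening: a diastolic pressure of 70 mmHg before 3 months is already high (>65), so 90 mmHg afterwards (>85) is not emergent, although 70 would be normal by the later limits. The SAP does not establish this as an error. By the baseline-age limits the child is high both times, and a child going from 70 to 90 without crossing any boundary would not be flagged either. It is a miss only if the later limits are taken as the yardstick. The false flags differ: an unchanged value is not emergent under either common set of limits.

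**Conclusion.** The point holds for false emergence. Read as a comparison of codes, the stated rules flag an unchanged value whenever a child crosses into a class with a tighter limit that excludes it. It is minor.

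The size is known only as exposure, on the assumptions of uniform ages and the boundary days given above. The number of children actually miscoded cannot be derived, because it depends on where their values lie, and some of those exposed would be emergent anyway.

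Two further inferences are not supported. The first is a bias between arms: crossing a boundary is balanced by randomisation in expectation. The second is a problem across all safety parameters: the QTcF, delta-QTc, SpO2 and body-temperature limits do not depend on age and are unaffected. Laboratory grades are outside the point, since the central laboratory supplies them and the SAP does not say which age it uses.

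**What to change.** Keep age at assessment for coding the abnormality itself. For the emergent flag only, add one sentence to Sections 6.3.1 and 6.4.1: for each post-baseline record, the baseline value is re-coded with the limits in force at that record, and the record is emergent only if its class is worse than the re-coded baseline. Apply this to Tables 25, 26 and 28. The same value under the same limits has the same code, so an unchanged value can no longer be emergent. The sentence also settles the yardstick where limits relax: the diastolic change from 70 to 90 mmHg would then be flagged.

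In the cross-tabulation, keep the single baseline class as coded at baseline, and footnote that the emergent column uses the re-coded baseline.

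The cost is SAP wording, one footnote and a small programming change, with no new data. For the few children who cross a boundary, the baseline and emergent columns may not reconcile: a child can go from normal to high without being emergent, or be high both times and emergent. The footnote should say so.
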